8. STATISTICAL CONSIDERATIONS

8.1 Sample Size

A sample size of 30 patients is targeted. Because each patient will likely contribute multiple mapped regions and ablation lines (e.g., roof line, posterior wall, CTI), this will yield a robust number of paired observations for both voltage and block concordance analyses.

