4. STUDY ENDPOINTS

4.1 Primary Endpoints

- **Concordance:** Percentage of agreement (presence vs. absence of bidirectional block) between the Optrell real-time vector assessment and standard activation remapping on a per-line basis.
- **Workflow Efficiency:** Difference in time (in minutes) required to confirm conduction block status using the Optrell vector method versus full activation mapping.

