8.2 Efficacy Analyses

• **Concordance of Block:** Agreement between the vector-based assessment and standard activation mapping will be evaluated using absolute percentage agreement and Cohen's Kappa statistic for inter-method reliability.

• **Time to Confirmation:** The time required to confirm conduction block will be compared between the two methods using a paired t-test or Wilcoxon signed-rank test, depending on the normality of the data distribution.

• **Voltage Comparison:** Paired continuous voltage data from the Octaray and Optrell catheters will be analyzed using Pearson or Spearman correlation coefficients. Furthermore, Bland-Altman analysis will be conducted to assess for systematic bias and establish limits of agreement between the two catheter designs.

• **Clinical Outcomes:** Freedom from arrhythmia at 12 months will be analyzed using Kaplan-Meier survival estimates.

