Optrell bipolar	 Yes  No	 Yes  No	_____ points
Optrell multipolar	 Yes  No	 Yes  No	_____ points

SECTION 3: PHASE 2 - ABLATION DETAILS

Variable	Data Entry
Ablation Energy Used	 RFA  PFA
PVI Performed?	 Yes  No
PVI Successfully Achieved?	 Yes  No
First Pass Isolation ?	 Yes  No
Linear Lesions Created (Check all that apply)	 Roof Line  Posterior Wall Isolation (PWI)  Cavotricuspid Isthmus (CTI)  Mitral Isthmus Line  Other: _____

SECTION 4: PHASE 3 - CONDUCTION BLOCK ASSESSMENT

(Complete this sub-section for EVERY linear lesion created. See Section 4b, 4c and 4d. Duplicate if necessary.)

Line Checked	 Roof Line  Posterior Wall Isolation (PWI)  Cavotricuspid Isthmus (CTI)  Mitral Isthmus Line  Other:	
Ablation Energy Used	 RFA  PFA	

Assessment Method	Time to Verify Block	Block Confirmed?
Optrell Vector Assessment (time to assess block by moving the catheter across the line to review vectors)	___ min : ___ sec	 Yes  No
Octaray Activation Mapping (time to create an activation map sufficient to determine presence or absence of block)	___ min : ___ sec	 Yes  No

Concordance for this line: ☐Yes (Methods agree) ☐No (Methods disagree)

Explain:_____

SECTION 5: ACUTE PROCEDURAL COMPLICATIONS (completed at hospital discharge)

Variable	Data Entry
None	
Pericardial Effusion / Tamponnade	
Stroke / TIA	

CONFIDENTIAL

Variable	Data Entry
Vascular Complication requiring intervention	
Phrenic Nerve Injury	
Prolongation of Hospitalization (>24 hours beyond the expected post-procedural course)	
Esophageal injury	

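### Section 8.1 counts several lines and regions per patient as robust paired data, and 8.2 names independent-pair methods with no allowance for clustering within patients

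*Protocol*

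**What the plan says.** Section 8.1 reads "A sample size of 30 patients is targeted". Its only support is the number of observations per patient: "Because each patient will likely contribute multiple mapped regions and ablation lines", it says, "this will yield a robust number of paired observations for both voltage and block concordance analyses". It gives no significance level, power, effect size, expected agreement, precision target, number of lines per patient or intra-patient correlation.

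The units of observation lie below the patient:

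- **Concordance (section 4.1):** agreement is taken "between the Optrell real-time vector assessment and standard activation remapping on a per-line basis".
- **Time (Appendix D, Section 4 of the procedural CRF):** the block result and the time for each method go on one form per line. The instruction is "Complete this sub-section for EVERY linear lesion created", and Sections 4b to 4d repeat the form.
- **Voltage (section 4.2):** amplitudes from the two catheters are paired by matched anatomical region.

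Section 8.2 fixes the methods. Block agreement "will be evaluated using absolute percentage agreement and" Cohen's kappa. Time to confirmation is to be "compared between the two methods using a paired t-test or Wilcoxon signed-rank test, depending on the normality of the data distribution". Voltage is handled by Pearson or Spearman correlation and Bland-Altman limits of agreement. The protocol names no patient-level summary, mixed model, cluster-robust variance, patient-level bootstrap or repeated-measures Bland-Altman.

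**The concern.** Lines made in one patient share the atrium, the operator, the rhythm and the mapping session. A patient in whom one method is slow or misleading on one line may well show the same on the next, so positive correlation within patients is plausible. If it is present, several lines from one patient carry less information than the same number from different patients, and 8.1 credits the study with more information than it has.

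Three results would then look too certain: the P value for time if the test is run on pooled lines, any interval reported for percentage agreement or kappa, and the inference on voltage bias and correlation. This matters because the synopsis and section 2.2 present the concordance and time results as grounds for doing without full-chamber remapping.

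**Working it through.** **The plan's own figure.** The target of 30 comes with no formula and no inputs, so it can be neither reproduced nor refuted. What can be checked is how far the pair count overstates the information.

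**Input from the protocol.** 30 patients (8.1).

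**Assumptions not in the protocol.** 2 to 4 lines per patient (the index CRF prints four line forms), 10 voltage regions per patient, ICC from 0 to 0.5, true agreement 90%, two-sided 5% level. The ICC is that of the analysed quantity: the time difference between methods, the agree/disagree result, or the voltage difference.

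**Formulas.** With m pairs per patient, the design effect is DE = 1 + (m − 1) × ICC and the effective number of pairs is 30m / DE. The approximate true error of a nominal 5% test is 2 × [1 − Φ(1.96/√DE)].

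Example, m = 3 and ICC = 0.3: DE = 1 + 2 × 0.3 = 1.6. Effective pairs = 90/1.6 = 56.2. Approximate error = 2 × [1 − Φ(1.96/√1.6)] = 12.1%. Simulation gives 12.2%.

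**Lines.** The type I error of the pooled paired t-test (4,000 runs) and the coverage of a naive 95% Wilson interval at 90% agreement (beta-binomial model, 20,000 runs) are simulated.

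| Lines per patient | ICC | Pairs | DE | Effective pairs | t-test type I error | Interval coverage |
|---|---|---|---|---|---|---|
| 2 | 0.1 | 60 | 1.1 | 54.5 | 6.1% | 94.3% |
| 2 | 0.3 | 60 | 1.3 | 46.2 | 8.4% | 92.0% |
| 2 | 0.5 | 60 | 1.5 | 40.0 | 10.0% | 89.6% |
| 3 | 0.1 | 90 | 1.2 | 75.0 | 7.5% | 92.7% |
| 3 | 0.3 | 90 | 1.6 | 56.2 | 12.2% | 87.8% |
| 3 | 0.5 | 90 | 2.0 | 45.0 | 16.5% | 83.8% |
| 4 | 0.1 | 120 | 1.3 | 92.3 | 8.3% | 92.4% |
| 4 | 0.3 | 120 | 1.9 | 63.2 | 14.8% | 85.2% |
| 4 | 0.5 | 120 | 2.5 | 48.0 | 21.6% | 78.9% |

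The Wilcoxon test behaves alike: with 3 lines, 7.0%, 12.3% and 15.7% at the three ICCs. At ICC 0 both tests stay near 5%, and coverage near ICC 0 is about 95%. A t-test on one mean difference per patient keeps 4.3 to 5.6% in every scenario.

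**Unequal numbers of lines.** Assume 1, 2, 3 and 4 lines in 15, 35, 30 and 20% of patients. Then E[k] = 2.55 and E[k²] = 7.45, and 30 × 2.55 = 76.5 lines are expected. DE = 1 + ICC × (7.45/2.55 − 1) = 1.19, 1.58 and 1.96 at ICC 0.1, 0.3 and 0.5, so the lines act like about 64, 49 and 39.

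**Effect on an agreement interval.** With 3 lines per patient and 90% agreement, the naive 95% interval on 90 lines is 82.1 to 94.6%. At the effective sizes it is 81.1 to 95.0%, 79.4 to 95.4% and 77.9 to 95.8%.

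**Voltage.** With 10 regions per patient there are 300 pairs. DE = 1 + 9 × ICC = 1.9, 3.7 and 5.5, so the effective numbers are 158, 81 and 55. A nominal 5% test of zero bias would have an approximate error of 15.5%, 30.8% and 40.3%.

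**The case against.** The strongest reply is that 8.2 names families of methods, not variance estimators. Kappa with a patient-level bootstrap is still kappa, a repeated-measures Bland-Altman is still Bland-Altman, and such choices can be left to an SAP, which is not at hand. Patient identifiers are on the CRFs, so clustering can be handled at analysis. This stands in part: the protocol never states independence, and a later plan could supply much of the remedy. But the pair-count argument in 8.1 is the protocol's own claim and the only basis for its sample size, and an SAP cannot make it true.

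A reader might infer more than the documents support:

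- **That all primary intervals and P values are wrong.** No interval is specified for concordance, and the only primary significance test named is the one for time. Positive correlation does not in itself invalidate the estimates of agreement or mean difference.
- **That the time test is certainly run on pooled lines.** The phrase "on a per-line basis" in 4.1 belongs to the concordance endpoint, and 8.2 names no unit for the time test. Time is recorded per line, but a test on one difference per patient would fit the text and be valid.
- **That all lines share one Octaray map, so correlation must be very high.** The CRF asks for a separate Octaray time for each line. The CTI line lies in the right atrium, and the pre-ablation forms list left and right atrial maps separately.
- **That redo lines are counted twice.** Section 7.4 requires the earlier lines to be assessed again at a redo but does not say that those pairs enter the primary analysis. This is an open point.
- **That the study has only 30 observations' worth of information.** The effective number lies between the patient count and the pair count.

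Choosing between t-test and Wilcoxon after a normality check is a separate matter and no part of this point.

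**Conclusion.** The point holds as a should-fix. Sections 8.1 and 8.2 together present within-patient pairs as the study's information and name methods whose standard inference ignores clustering. Followed as written on pooled lines and regions, they would overstate precision.

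For 2 to 4 lines per patient, type I error of the time test is about 6 to 8% at ICC 0.1, 8 to 15% at 0.3 and 10 to 22% at 0.5. Coverage of a naive 95% interval at 90% agreement is about 92 to 94%, 85 to 92% and 79 to 90%. These figures rest wholly on assumed lines, regions and correlations: the effect is negligible near ICC 0 and material from about 0.3 with 3 or 4 lines. It does not rank higher because the study is observational, states no success threshold, and can be corrected at analysis with the data already planned.

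**What to change.** In 8.2, name the patient as the cluster for every per-line and per-region analysis:

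- **Agreement and kappa:** report intervals from a bootstrap that resamples patients.
- **Time:** use a mixed model with a random patient intercept, or a paired test on one mean difference per patient, and state which.
- **Voltage:** use repeated-measures forms of Bland-Altman analysis and correlation.
- **Redo procedures:** keep these pairs out of the primary analysis, or place them in the same patient's cluster.

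In 8.1, replace the pair-count claim with a statement that lines and regions are clustered within 30 patients and that precision is therefore lower than the number of pairs implies. Give the expected precision over a stated ICC range, with the assumed lines per patient. For example, at 90% agreement with 3 lines each, the 95% interval runs from 81.1 to 95.0% at ICC 0.1 and from 77.9 to 95.8% at ICC 0.5.

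The cost is wording, slightly more analysis work and somewhat wider intervals. No additional patients or data are needed. The change is most credible if made before results are seen.

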8.2 Efficacy Analyses

• **Concordance of Block:** Agreement between the vector-based assessment and standard activation mapping will be evaluated using absolute percentage agreement and Cohen's Kappa statistic for inter-method reliability.

• **Time to Confirmation:** The time required to confirm conduction block will be compared between the two methods using a paired t-test or Wilcoxon signed-rank test, depending on the normality of the data distribution.

• **Voltage Comparison:** Paired continuous voltage data from the Octaray and Optrell catheters will be analyzed using Pearson or Spearman correlation coefficients. Furthermore, Bland-Altman analysis will be conducted to assess for systematic bias and establish limits of agreement between the two catheter designs.

• **Clinical Outcomes:** Freedom from arrhythmia at 12 months will be analyzed using Kaplan-Meier survival estimates.

8.3 Data Management and Protocol Compliance

Protocol compliance will be strictly monitored throughout the 12-month follow-up period. Any required clinic visits, ECGs, or 24-hour Holter monitors that are missed entirely, or completed outside the designated ± 14 -day window, will be documented as protocol deviations. The overall

follow-up compliance rate will be reported in the final analysis to validate the capture of the clinical efficacy endpoints.

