- 185 • Any other serious adverse event related to the procedure

186

187 **Safety Follow-Up Period**

188 Formal protocol-mandated safety follow-up will extend through 7 days after the procedure or until
189 hospital discharge, whichever occurs later.

190 All AEs and SAEs occurring during this period will be documented in the CRF and reviewed by
191 the Medical Monitor.

192

193 **7.2 Clinical Follow-Up and Rhythm Monitoring**

194 Patients will undergo highly structured longitudinal follow-up to monitor for clinical and
195 subclinical arrhythmia recurrence and symptom status.

196 **Clinic Visits:**

CONFIDENTIAL

Patients will be evaluated at the following time points after the ablation procedure:

- 1 month \pm 14 days
- 3 months \pm 30 days
- 6 months \pm 30 days
- 9 months \pm 30 days
- 12 months \pm 30 days

Visits at 3 and 12 months will be conducted in person, while other visits may be conducted in person or via telemedicine, depending on clinical circumstances.

During these visits, the following information will be collected:

- Symptoms suggestive of arrhythmia recurrence
- Medication use, including antiarrhythmic drugs and anticoagulation
- Interval hospitalizations or cardiovascular events
- Standard ECG documentation when available

Rhythm Monitoring:

To systematically detect symptomatic and asymptomatic arrhythmia recurrence, patients will undergo scheduled ambulatory rhythm monitoring during follow-up.

A minimum of three 48-hour Holter monitors will be performed at:

- 3 months \pm 30 days
- 6 months \pm 30 days
- 12 months \pm 30 days

Additional rhythm monitoring (Holter, event monitor, or ECG) may be performed at the treating physician's discretion if symptoms suggest arrhythmia recurrence.

Recurrence of atrial arrhythmia will be defined as documented AF or atrial tachycardia lasting \geq 30 seconds after the standard 2-month blanking period.

Community-Based Testing: To facilitate protocol compliance, both the 12-lead ECGs and the 24-hour Holter monitors may be performed locally at the patient's primary care clinic (Kupat Holim). The study coordinator is responsible for retrieving and analyzing these community-based reports and logging the data into the study database.

228

229 **7.3 Post-Procedure Antiarrhythmic Drug Management**

230 The use of AADs following the ablation procedure will be at the discretion of the treating
231 electrophysiologist and managing physician, in accordance with routine clinical practice.

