12. APPENDIX A - STUDY FLOWCHART

13. APPENDIX B- Schedule of Assessments

Study Activity	Screening / Pre- Procedure	Procedure Day	Post-Procedure / Discharge	1 Month	3 Months	6 Months	9 Months	12 Months
Informed consent	-----X-----							
Eligibility confirmation	X	X						
Demographics and medical history	X							
Arrhythmia Classification (PAF / PerAF / Flutter)	X							
Baseline medications	X		X	X	X	X	X	X
Standard Ablation according to protocol		X						
Procedural safety assessment		X	X					
Adverse event assessment			X	X	X	X	X	X
ECG			X	X	X	X	X	X
AAD documentation			X	X	X	X	X	X
48-hour Holter					X	X		X
Arrhythmia recurrence assessment				X	X	X	X	X
Documentation of redo ablation (if applicable)					X	X	X	X

14. Appendix C – AE / SAE Form

Field	Description / Options
Study ID	
Hospital MRN	
Event number	
Event classification	 AE  SAE
SAE Category	
SAE type	 Pericardial effusion / tamponade  Stroke / TIA  Vascular complication requiring intervention  Phrenic nerve injury  Esophageal injury  Heart failure exacerbation requiring treatment  Prolonged hospitalization (>24h)  Other (specify)
Event description	
Date of onset	
Date of resolution	
Severity	 Mild  Moderate  Severe
Seriousness criteria	 Death  Life-threatening event  Prolonged hospitalization  Persistent disability  Medically significant event
Relationship to procedure	 Related to procedure  Possibly related to study mapping protocol  Unrelated
Action taken	 Observation  Medication  Intervention  Hospitalization  Other
Outcome	 Resolved  Ongoing  Resolved with sequelae  Death
Reported to Medical Mon	 Yes  No
Date reported	
Investigator signature	

15. Appendix D – Procedural CRF**SECTION 1: DEMOGRAPHICS AND CLINICAL HISTORY/DATA**

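### Section 8.3 scores follow-up against a 14-day window and a 24-hour Holter, whereas section 7.2 allows 30 days from month 3 on and requires 48-hour Holters

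*Protocol*

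**What the plan says.** Section 8.3 states the compliance rule. It logs as protocol deviations "Any required clinic visits, ECGs, or 24-hour Holter monitors that are missed entirely, or completed outside the designated" window, and gives that window as 14 days either side, with no distinction by time point or type of item. It then says that the overall follow-up "compliance rate will be reported in the final analysis to validate the capture of the clinical efficacy endpoints".

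The schedule being policed is in section 7.2. Under "Patients will be evaluated at the following time points after the ablation procedure" it lists month 1 with 14 days either side, and months 3, 6, 9 and 12 with 30 days either side. For rhythm monitoring it says "A minimum of three 48-hour Holter monitors will be performed at" months 3, 6 and 12, each with 30 days either side. ECGs get no window of their own; the visit list asks for "Standard ECG documentation when available".

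On Holter length, Appendix B lists a "48-hour Holter" at months 3, 6 and 12, and the follow-up CRF (Appendix E, Section 3) asks whether a 48-hour Holter was performed. The community-testing paragraph of 7.2, however, says that "24-hour Holter monitors may be performed locally", and 8.3 uses the same 24-hour figure.

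Appendix E, Section 1 asks whether the visit fell within the protocol window and labels the negative answer a protocol deviation. It does not say which window applies.

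**The concern.** Two values in 8.3 disagree with the schedule that the section is meant to enforce.

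The first is the window. A month-6 Holter done 20 days late is on time under 7.2 and a deviation under 8.3. Staff completing the CRF have two rules and no instruction on which to use. Because the compliance rate is offered as evidence that recurrences were captured, a rate that depends on which section was applied does not serve that purpose. Applied as written, 8.3 understates compliance with the 7.2 schedule.

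The second is the recording length. The 24-hour wording sits in the paragraph that tells community clinics what they may do and in the paragraph that says what is scored. A clinic could follow that text, record 24 hours and be counted as compliant under 8.3, although the monitoring requirement asks for 48. Recurrence means a documented episode of at least 30 seconds after the blanking period, so less scheduled recording means less chance of finding asymptomatic episodes. Recording lengths that differ between patients would also make the 12-month Kaplan-Meier estimate harder to interpret.

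**Working it through.** The plan gives no figure of its own to reproduce. The check sets the two sections side by side and counts how much of the schedule lies in the conflict.

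**Windows compared**

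| Item | Section 7.2 | Section 8.3 |
|---|---|---|
| Visit, month 1 | ±14 days | ±14 days |
| Visits, months 3, 6, 9, 12 | ±30 days | ±14 days |
| Holters, months 3, 6, 12 | ±30 days, 48 h | ±14 days, 24 h |
| ECGs | no window of their own | ±14 days |

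Only one of the five visits, and none of the Holters, has the same window in both sections.

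**Days in conflict at each time point from month 3 on**

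- Permitted by 7.2: 2 × 30 + 1 = 61 days.
- Permitted by 8.3: 2 × 14 + 1 = 29 days.
- On time under 7.2 but a deviation under 8.3: 61 − 29 = 32 days (days 15 to 30 on each side).
- Share: 32/61 = 52.5%.

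This is a share of calendar days. It would be the expected share of misclassified items only if timing were uniform over the 7.2 window, which the protocol gives no reason to assume. With timing closer to target it falls towards 0%.

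**Items exposed to the conflict, for the 30 patients in section 8.1**

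- Visits: 30 × 5 = 150, of which 30 × 4 = 120 have the 30-day window.
- Holters: 30 × 3 = 90, all with the 30-day window.
- Visits and Holters together: (120 + 90)/(150 + 90) = 210/240 = 87.5%.

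A second count adds the ECGs at the five follow-up visits in Appendix B, leaving out the discharge ECG. It assumes that an ECG takes the window of its visit.

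- ECGs: 30 × 5 = 150, of which 120 fall at visits with the 30-day window.
- All items: (120 + 120 + 90)/(150 + 150 + 90) = 330/390 = 84.6%.

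Both counts are shown because 8.3 scores required ECGs while 7.2 asks for them only if available.

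**Scheduled Holter time per patient**

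- Three 48-hour recordings: 3 × 48 = 144 h.
- Three 24-hour recordings: 3 × 24 = 72 h, the extreme case.

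**With 8.3 aligned to 7.2**, no item done within its 7.2 window is logged as a deviation.

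**The case against.** The strongest reply is that little depends on this. Nothing in section 8.2 uses deviation status: no analysis set, exclusion, censoring rule or test refers to it. The window conflict affects one descriptive rate, and in the conservative direction. It does not change which arrhythmias are counted. All of that stands, and it is why the point is a correction and not a threat to the trial's conclusions.

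A second reply is that the 48-hour requirement is clear enough. It appears in the monitoring paragraph of 7.2, in Appendix B and in Appendix E, where a 24-hour recording should properly be entered as a 48-hour Holter not performed. The CRF has no field for hours recorded, but 7.2 says "The study coordinator is responsible for retrieving and analyzing these community-based reports", so the length could be recovered from the report. This makes 48 hours the likelier intent. It does not remove the problem, because the community-testing and scoring text both say 24, and 8.3 read on its own would pass a 24-hour recording.

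A third reply is that 8.3 speaks of strict monitoring, so a tighter window may be intended. The documents do not exclude that. But 7.2 sets its windows item by item, for visits and Holters separately, and a deviation rule stricter than the schedule it enforces would need to be stated as such. Nor does treating the word designated as a pointer to 7.2 help, because 8.3 gives the number itself.

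Finally, the 52%, 85% and 88% figures measure exposure, not effect. That is correct, and they should be read only in that way.

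**Conclusion.** The concern holds. Section 8.3 contradicts 7.2 on the window for four of five visits and all three Holters. It also contradicts 7.2, Appendix B and Appendix E on Holter length. The community-testing paragraph puts the same length conflict inside 7.2 itself.

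The practical size is modest. The understatement of compliance depends on actual timing and is zero if every date falls within 14 days of target. The Holter conflict matters only if some recordings are made at 24 hours, and then only for scheduled monitoring behind a secondary endpoint in a single cohort. Concordance and time to confirmation are untouched. The change should nevertheless be made, because both values are fixed wrongly in the current text and the compliance rate is meant to support the recurrence results. The ECG-inclusive count rests on the assumption that ECGs take their visit's window; the other counts need no assumption beyond the planned 30 patients completing the schedule.

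**What to change.** Change three phrases:

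1. In 8.3, replace the 14-day window with a reference to the visit-specific windows of section 7.2.
2. In 8.3, change the Holter length from 24 to 48 hours.
3. In the community-testing paragraph of 7.2, make the same change from 24 to 48 hours.

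If the sponsor does intend a tighter window, 7.2 should be changed instead, so that only one rule remains. An hours-recorded field in Appendix E, Section 3 is optional but would show short recordings without going back to the report.

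The cost is close to nothing if this is done before follow-up data accrue. Later, deviations already logged would have to be re-adjudicated, and recording time lost to 24-hour Holters could not be recovered.
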